#### Inclusion Criteria:

All patients initially identified by their surgeon as potentially STAR eligible (this occurring prior to both Physiotherapy and Anesthesiology STAR assessments) are eligible as data sources in this study.

#### Exclusion Criteria:

It is possible that a STAR eligible patient may not ever have come to surgery. Such patients would be excluded from the study as all patients have to have had a surgical procedure performed to be included.

#### Number of Patients:

As the specific criteria to be a STAR Patient at VGH/UBCH is new and not formerly used elsewhere, it is unknown how many patients would be needed to show a statistically significant difference between the two groups. Indeed, one of the main purposes of this study is to act as a

preliminary indicator for the rate of return to hospital of such patients to inform a future prospective study's appropriate sample size.

To this end, we anticipate that up to 120 patients will have been through the STAR screening process by Oct 1, 2019 and that this should allow ample opportunity to compare the two groups.

#### De-identification & Data Management:

Each patient's personal identifiers (Name & Date of Birth) will be linked to a Patient Study Number. The matching of personal identifiers to a Patient Study Number will occur only on one list, retained only by the PI and separate to all other data collection spreadsheets. Data collected to fulfill the Primary and Secondary Outcomes will only contain the Patient Study Numbers, with no personal identifiers. The personal identifiers will be used by study personnel to attain the patient's paper VGH/UBCH charts, as well as being the source to the patient's BC Care Connect chart. We reiterate that none of these personal identifiers will appear on any of the Primary & Secondary Outcomes data collection spreadsheets.

Data linking the patient's personal identifiers and the Patient Study Numbers will be retained only by the PI. This linked data will be stored only on a password protected personal computer hard drive retained by the PI, and will not be stored on any "Cloud" or "off site" Server. Neither will it be shared electronically with any of the study personnel. Paper copies of the linked data will be handed directly to Study Personnel by the PI for the purpose of data collection. These paper copies will be destroyed once the data collection is completed by Study Personnel.

Deidentified data will be collected onto a spreadsheet and retained in Redcap. This will be shared amongst Study Personnel via online password protected access. Included with this submission are the "Column Headings" for the five data collection spreadsheets that will be used in this study, one of which is the "De-Identifier" spreadsheet.

#### Statistical Analysis:

A Statistician, affiliated with the Dept of Statistics at UBC, will be retained to run the comparative analysis between the rates of return to hospital between the two groups, as well as characterizing the group's demographics of age and gender. The Statistician will be blinded to all personal identifiers.

#### INVESTIGATION TEAM:

The Principle Investigator in this study ([name]) is ultimately responsible for all matter of data collection and processing. All others collecting data will be either members of the Dept of Anesthesia at VGH & UBCH, or Medical Students from a Canadian University and trained by the Principle Investigator in the process of data collection. Any Medical Students involved in this project will be granted the right to participate in data collection by the Dept of Anesthesia prior to commencing.

#### ETHICAL REQUIREMENTS:

The study will be performed in accordance with the principles stated in the Tri-Council Policy Statement: Ethical Conduct for Research Involving Humans (TCPS2).

The Principle Investigator is responsible for informing the ethics committees of any major amendments to the protocol as per local requirements. All correspondence with the committee will be filed by the Principle Investigator.

#### CONCLUSION:

This retrospective cohort quality assurance project seeks to make some preliminary assessments of the STAR Program's rate of return to hospital up to 30 days following primary hip arthroplasty. Specifically, the rates of return to hospital are compared between those patients discharged from hospital on the day of their surgery, and those who stayed at least one night in hospital before being discharged. Our objective is to use this comparison as a quality assurance measure of safety for discharge same day of patients who meet our clinical criteria to do so.

Incidence of 30 Day Return to Hospital Following Same Day Discharge Total Hip Arthroplasty

- Data Collection Spreadsheet Headings & Statistical
Analysis Plan -

[name], FRCPC
VGH/UBCH Dept of Anesthesiology & Perioperative Care
Vancouver General Hospital & UBC Hospital
Vancouver, BC, Canada

Oct 6, 2019

Incidence of 30 Day Return to Hospital Following Same Day Discharge Total Hip Arthroplasty

STAR STUDY SPREADSHEET COLUMN HEADINGS & STATISTICAL ANALYSIS PLAN:

A) SPREADSHEET COLUMN HEADINGS:

Data from chart reviews will be collected into the following five spreadsheets.

Spreadsheet 1 will be the De-identifier spreadsheet, the only data collection apparatus containing any personal identifiers. This spreadsheet will be retained only by the PI and stored on a password protected personal computer without any “off-site” or cloud based storage. Spreadsheet 1 information will be distributed to Research Personnel in paper form only.

Spreadsheet 2 will be an all patients list that will segregate patients into one of the three cohorts being studied.

Spreadsheet 3 will retain data from the “STAR Eligible & Discharged Same Day” cohort.

Spreadsheet 4 will retain data from the “STAR Eligible, NOT Discharged Same Day” cohort.

Spreadsheet 5 will retain data from the “NOT STAR Eligible” cohort.

The Data collection venue for de-identified Spreadsheets 2 to 5 will be Redcap (©).

1) De-Identifier:

Patient Study Number	MRN	Date of Surgery	Last Name	First Name	Date of Birth	Age	Gender

2) All Patient List:

Patient Study Number	Removed From STAR Pathway (Y or N)	Discharged On Day Of Surgery (Y or N)

3) Discharged Day of Surgery:

Patient Study Number	PACU Arrival Time	Discharge Home Time	Duration of Hospital Stay (min)	Hospital Re-encounter (Y or N)	Days Post-op at time of Re-encounter	Nature of Surgical Problem/Complication	Anesthesia Checklist Complete (Y or N)

4) NOT Discharged Day of Surgery:

Patient Study Number	Reason Not D/C'd Same Day - General	Reason Not D/C'd Same Day - Specific	Days In Hospital Post-Op	Hospital Re-encounter (Y or N)	Days Post-op at time of Re-encounter	Nature of Surgical Problem/Complication	Anesthesia Checklist Complete (Y or N)

5) Removed from STAR Pathway Prior to Surgery:

Patient Study Number	Reason for STAR Removal - General	Reason for STAR Removal - Specific	Days in Hospital Post-Op	Hospital Re-encounter (Y or N)	Days Post-op at time of Re-encounter	Nature of Surgical Problem/Complication	Anesthesia Checklist Complete (Y or N)

B) STATISTICAL ANALYSIS PLAN:

Statistical analysis will focus on the Primary and Secondary Outcomes (incidence of 30 and 7 day return to hospital encounters for surgical related assessment, complications &/or treatments respectively). Demographic data of patient age and gender will also be statistically analyzed.

Statistical analysis will be conducted with the aid of a Statistician affiliated with the UBC Department of Statistics, and the use of "R" software for statistical computations (© "The R Foundation"). Data will be reported as percentages or means +/- confidence intervals as appropriate.

Demographic data (age and gender) will be statistically compared between the three cohorts as follows. Age, being a numerical discrete variable, will be compared using Kruskal-Wallis Rank Sum Test. Gender, being a binomial variable, will be compared using Pearson's Chi-Squared test with Yates Correction for Continuity.

The Primary Outcome Statistical Analysis will be conducted as follows.

The two-tailed "null" (H_0) and "alternate" (H_A) hypothesis testing is as follows:

H_0 = Incidence of 30 day return to hospital not significantly different between compared groups

H_A = Incidence of 30 day return to hospital is significantly different between compared groups

Data from each of the cohorts will be plugged into the following three (A, B & C) 2 X 2 outcome tables:

Tables For Comparative Statistics:

A)

	Number of Patients with 30 Day Encounters or Complications	Number of Patients with NO 30 Day Encounters or Complications
Eligible & Same Day Discharged		
Eligible & NOT Same Day Discharged		

B)

	Number of Patients with 30 Day Encounters or Complications	Number of Patients with NO 30 Day Encounters or Complications
Eligible & Same Day Discharged		
Not Eligible for Same Day Discharge		

C)

	Number of Patients with 30 Day Encounters or Complications	Number of Patients with NO 30 Day Encounters or Complications
Eligible & Same Day Discharged		
Both: Eligible & NOT Same Day Discharged AND Not Eligible for Same Day Discharge		

The categorical dichotomous outcome data from each of these 2 X 2 tables will be assessed for statistically significant differences using Pearson's Chi-Squared test with Yates Correction for Continuity, unless expected values are less than 10 (with degrees of freedom of 1) in which case Fisher's Exact Test will be used. Statistical significance is set at $\alpha = 0.05$.

Secondary Outcome analysis for 7 day return to hospital comparison will use the same statistical formatting, substituting the 7 day rate for the 30 day rate in each of these tables.

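### Can the three-cohort age and gender comparison be run, given where those variables are recorded and the Yates-corrected test named for gender?

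*SAP*

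**What the plan says.** The protocol (Study Design) makes comparison of age and gender between cohorts a secondary goal. Its Statistical Analysis section gives that work to a statistician and adds: "The Statistician will be blinded to all personal identifiers".

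The SAP, part B, sets the comparison across three groups: "Demographic data (age and gender) will be statistically compared between the three cohorts as follows". For age: "Age, being a numerical discrete variable, will be compared using Kruskal-Wallis Rank Sum Test". For gender: "Gender, being a binomial variable, will be compared using Pearson's Chi-Squared test with Yates Correction for Continuity". A small-count rule appears only with the 2 x 2 outcome tables: "unless expected values are less than 10 (with degrees of freedom of 1) in which case Fisher's Exact Test will be used".

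The SAP, part A, lists the columns of five spreadsheets. Age and Gender appear on Spreadsheet 1 alone, beside study number, MRN, date of surgery, names and date of birth. Of that sheet it says "Spreadsheet 1 will be the De-identifier spreadsheet, the only data collection apparatus containing any personal identifiers" and "This spreadsheet will be retained only by the PI"; research personnel receive its contents on paper. Spreadsheets 2 to 5, kept in REDCap, carry the study number and the cohort or outcome fields, with no age or gender column.

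**The concern.** On a first reading the plan promises an analysis that its own data set does not support. The statistician works from de-identified sheets, and none of the four holds age or gender. The one sheet that does is closed to everyone but the investigator, apart from paper copies that are later destroyed. No step is described that carries the two variables across. This matters because the cohorts are formed by eligibility and discharge decisions, not by randomisation, and age and gender are the only baseline characteristics planned for comparison.

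The gender test also looks misnamed. Yates' correction adjusts a statistic on 1 degree of freedom. If an analyst applied a similar correction to all cells of the three-cohort table, the test would become too conservative and could hide an imbalance. If the software dropped the correction, the report would name a test that had not been run.

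**Working it through.** The documents give no power, sample size or p-value for this comparison, so there is no figure of theirs to reproduce.

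**1. Can age and gender reach the analysis?**

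- Spreadsheet 1 holds study number, age and gender. Age has its own column, separate from date of birth.
- Spreadsheet 2 holds study number and the two yes/no fields that define the cohort.
- The study number is common to both, so the join needs three fields from Spreadsheet 1 and nothing that names a patient.
- The protocol (De-identification & Data Management) defines the personal identifiers as name and date of birth. Its bar on electronic sharing covers the data linking those identifiers to study numbers. A list of study number, age and gender is not that link.
- The statistician is blinded to identifiers, so receiving this list does not break the blinding.
- The paper copies that are destroyed are those given to data collectors. The investigator keeps the master, so no age or gender data are lost.

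**2. What does the named gender test do?**

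Degrees of freedom = (rows − 1)(columns − 1) = (3 − 1)(2 − 1) = 2. Kruskal-Wallis, named for age, is correct for three groups.

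Inputs: cohort sizes 24, 19 and 35 from the protocol's Background (24 + 19 + 35 = 78). The gender split is an assumption, since the documents give none: 8/24, 11/19 and 22/35 in one gender, 41 of 78 overall.

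Expected counts, n × 41/78 and n × 37/78:

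| Cohort | Observed | Expected | Expected, other gender | Difference |
|---|---|---|---|---|
| 24 | 8 | 12.615 | 11.385 | −4.615 |
| 19 | 11 | 9.987 | 9.013 | 1.013 |
| 35 | 22 | 18.397 | 16.603 | 3.603 |

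X² = Σ d²(1/E₁ + 1/E₂) = 3.560 + 0.217 + 1.487 = 5.263 after rounding. On 2 df, p = exp(−5.263/2) = 0.072.

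R's `chisq.test` on this table returned X² = 5.2634, df = 2, p = 0.07196 with the correction requested and again without it, and labelled both outputs as plain Pearson. On a 2 x 2 table (8/16 against 33/21) the correction does act: X² falls from 5.142 to 4.088, and p rises from 0.023 to 0.043.

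**3. What if a correction were forced by hand?**

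Taking 0.5 off every absolute difference gives X² = 3.989, p = 0.136. Simulated type I error at a nominal 5%, at 24/19/35 (200,000 tables per setting):

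| Assumed gender proportion | Plain Pearson | Forced correction |
|---|---|---|
| 0.3 | 0.051 | 0.020 |
| 0.4 | 0.050 | 0.022 |
| 0.5 | 0.050 | 0.022 |

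Scaled to the 120 patients anticipated in the protocol, the cohorts are 24 × 120/78 = 37, 19 × 120/78 = 29 and 35 × 120/78 = 54. With a 50% split, size is 0.052 plain and 0.026 forced. With an assumed 60/45/30% split, power is 0.739 plain and 0.646 forced.

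The forced version is clearly worse, but it needs a hand-coded six-cell adjustment that the SAP does not ask for and R does not perform.

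**4. Is an exact fallback needed for gender?**

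The smallest expected count in the example is 9.0, and it was 8.8 to 9.3 across the four splits tried. Plain Pearson held its size at 0.050 to 0.051 at these cohort sizes, so an exact test would gain nothing here.

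**The case for a change.** The strongest case for a change is that a secondary goal should have a written data path. The SAP says the contents of Spreadsheet 1 go to research personnel on paper only, so an electronic extract for R, even without names or dates of birth, sits awkwardly with that rule. The repair would be cheap: two columns on Spreadsheet 2 and one corrected sentence. The gender test is also mislabelled on any reading.

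What stands is that the transfer step is undescribed, its form needs squaring with the paper rule, and Yates is the wrong name for a test on 2 df. What does not stand is that the analysis is blocked. The investigator holds the data, is responsible under the protocol for their collection and processing, and works with the statistician on the analysis. The paper rule concerns how the sheet's contents travel; it does not remove age and gender from the study. Nor would a failure here spoil an adjusted comparison of return rates, because none is planned: the SAP specifies unadjusted 2 x 2 tables only.

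**Conclusion.** No change follows. The data path is a gap that the investigator would fill in the obvious way, through the shared study number and without releasing an identifier as the protocol defines it. The Yates wording is a slip with no numerical effect in the named software, since the test that R runs is already the uncorrected Pearson test on 2 df. The age test is correctly chosen.

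The comparison is descriptive. It does not enter the 30-day or 7-day analyses, and no decision depends on it. The losses of size and power under a forced correction are real but belong to a procedure outside the plan.

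This rests on three assumptions: that the analysis uses R's standard function, as the SAP's choice of software implies; that gender proportions lie roughly between 0.3 and 0.5, so that expected counts stay near 9 or not far below; and that age in years and gender are not treated as identifiers, which matches the protocol's own list.
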